## **BACKGROUND**

Chronic pain is one of the common problems in older adults, affecting their physical ability, treatment satisfaction, quality of life and psychosocial functioning. Various types of exercises have shown to have a positive impact on physical well-being, but more improvements on pain outcomes is observed with psychological interventions. Among the different behavioural therapies, Acceptance and Commitment Therapy (ACT) holds the key behaviours in the adaption and prolonged effect in chronic pain. Previous study has shown benefits of combining ACT and Exercise, but the effectiveness is yet unknown. We aim to examine the effectiveness of this method with the intention of enhancing the overall well-being of older adults with chronic pain.

## **OBJECTIVES**

The objective is to establish evidence of Acceptance and Commitment Therapy (ACT) in combination with exercise in:

Primary Outcomes

- 1) Reducing pain intensity and interference;
- 2) Reducing depression;

Secondary Outcomes

- 3) Reducing anxiety;
- 4) Increasing psychological flexibility;
- 5) Increasing pain-related self-efficacy;
- 6) Increasing quality of life;
- 7) Increasing physical functioning

## **METHODS**

### Design

This study adopts a cluster randomized trial design comparing older adults with chronic pain receiving ACT and exercise intervention to two arms: 1) art and exercise; and 2) treatment as usual (control group). 15-20 elderly from 10 different mental health service centres will be randomized to the experimental, sham, or active control group.

### Participants

The effect size from previous literature and pilot data (0.25), an alpha=0.05, and power=0.8 was used to derive the total sample size of 135 participants. Assuming 10% attrition, total sample size = 150. Older adults with chronic pain (n=150) recruited from collaborating NGOs will be randomized into 3 different arms: 1) ACT and exercise; 2) art and exercise; and 3) treatment as usual.

Inclusion criteria are:

- age 60 years or above; and
- have depressive symptoms of mild level or above (PHQ > 5)
- have chronic pain (>3 months)
- able to give informed consent to participate

Exclusion Criteria:

- known history of autism, intellectual disability, schizophrenia-spectrum disorder, bipolar disorder, Parkinson's disease, or dementia
- (temporary exclusion criteria) imminent suicidal risk difficulty in communication
- have had stroke, fracture, cardiovascular disease, cardiovascular surgery, artery disease, surgery on vertebrae, and knee replacement in the past 6 months
- physical activity prohibited by a medical professional

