## **Data Analysis**

Data will be analysed using a pre-post analysis based on different time points. For the main outcome measures of depressive symptoms/risks, wellbeing, and personal recovery, mixed ANOVA will be used to assess changes from T0/Intake to T1/exit between the two groups. To test for sustained effect after completion of intervention, mixed ANOVA will be used to assess depressive symptoms/risks, wellbeing, pain acceptance, physical ability, and symptoms of pain from T1/Exit to T2/FU within- and between- subjects. All results will be reported with the appropriate effect sizes, along with statistical significance and confidence intervals.

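### The protocol declares a cluster randomised trial in 10 centres, but the sample size states no clustering term, so the 80% power is not supported for that design

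*Protocol*

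**What the plan says.** **Design** (Methods): "This study adopts a cluster randomized trial design", with three arms. The next sentence says "15-20 elderly from 10 different mental health service centres will be randomized to the experimental, sham, or active control group". Its grammatical subject is the older adults, not the centres.

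**Participants** (Methods): the inputs are an effect size of 0.25 taken from earlier literature and pilot data, and "an alpha=0.05, and power=0.8 was used to derive the total sample size of 135 participants". The only adjustment is "Assuming 10% attrition, total sample size = 150". The section adds that the 150 older adults "recruited from collaborating NGOs will be randomized into 3 different arms", which again reads as allocation of persons.

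**Data Analysis**: "mixed ANOVA will be used to assess changes from T0/Intake to T1/exit between the two groups". No centre term is named.

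The protocol gives no ICC, design effect or number of centres per arm. It does not say whether 0.25 is Cohen's f, a standardised mean difference or something else, and it names no test for the sample size.

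**The concern.** When centres are allocated, participants in the same centre tend to resemble one another, and the comparison of arms rests on variation between centres. Two costs follow. The variance of the comparison grows by the design effect, and with 10 centres in three arms only 10 − 3 = 7 between-centre degrees of freedom remain. Neither cost appears in the derivation of 135.

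If individuals are allocated instead, those costs do not apply in this form, but the cluster label in Design is then wrong. The two sections cannot both stand as written.

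The protocol makes an unqualified claim of 80% power that a reader cannot verify. If true power is well below that, a null result could not be read as evidence against the planned effect.

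**Working it through.** **Inputs from the protocol.** 10 centres and 3 arms (Design); effect size 0.25, alpha 0.05, power 0.80, 135 evaluable, 10% attrition, 150 enrolled (Participants); comparison of change from T0 to T1 by mixed ANOVA (Data Analysis).

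**Assumptions added here.** Equal arms; 0.25 read as Cohen's f; ICC of 0.01, 0.02, 0.05 or 0.10. All power values use the noncentral F distribution at alpha 0.05 with 2 numerator degrees of freedom (df) and noncentrality λ.

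**Step 1. The attrition step reproduces.** 135 / (1 − 0.10) = 150.

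**Step 2. 135 does not follow from the stated inputs alone.**

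- One-way ANOVA, three groups: λ = N f². At N = 135, λ = 135 × 0.0625 = 8.44 on (2, 132) df, power 0.73. Reaching 80% takes N = 159 (power 0.805).
- ANCOVA: λ = N f² / (1 − r²). With r = 0.4, N = 135 gives λ = 8.4375 / 0.84 = 10.04 and power 0.808.
- Repeated-measures group main effect, two times: λ = 2 N f² / (1 + r). With r = 0.7, N = 135 gives λ = 16.875 / 1.7 = 9.93 and power 0.803.
- Group-by-time interaction, two times: λ = 2 N f² / (1 − r). The N needed is 81, 60, 42 or 27 at r = 0, 0.3, 0.5 or 0.7.
- The interaction N at r = 0 with a clustering inflation: 135 / 81 = 1.67, which at 13.5 per centre is an ICC of 0.67 / 12.5 ≈ 0.053.

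The routes found to 135 each need an input that the protocol does not state: a correlation near 0.4, a correlation near 0.7, or a design effect of 1.67.

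**Step 3. Design effect.** Analysed cluster size is 135 / 10 = 13.5, so DE = 1 + (13.5 − 1) × ICC = 1 + 12.5 × ICC.

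**Step 4. Reading (a): 135 independent participants give exactly 80%.** On (2, 132) df this needs λ = 9.86. Divide by DE and re-evaluate:

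| ICC | DE | λ / DE | Power, (2, 132) df | Power, (2, 7) df |
|---|---|---|---|---|
| 0 | 1.000 | 9.86 | 0.80 | 0.61 |
| 0.01 | 1.125 | 8.76 | 0.75 | 0.56 |
| 0.02 | 1.250 | 7.89 | 0.70 | 0.51 |
| 0.05 | 1.625 | 6.07 | 0.58 | 0.41 |
| 0.10 | 2.250 | 4.38 | 0.44 | 0.31 |

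**Step 5. Reading (b): 0.25 is f for the T0-to-T1 group-by-time interaction.** The unclustered λ is 2 × 135 × 0.0625 / (1 − r) = 16.875 / (1 − r). Divide by DE, taking the ICC as that of the change score, and evaluate on (2, 7) df:

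| ICC | Power, r = 0 | Power, r = 0.5 |
|---|---|---|
| 0.01 | 0.79 | 0.98 |
| 0.02 | 0.75 | 0.96 |
| 0.05 | 0.63 | 0.91 |
| 0.10 | 0.49 | 0.79 |

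On (2, 7) df, 80% needs λ = 15.26. The largest design effect that 135 can carry is (16.875 / (1 − r)) / 15.26:

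| r | Largest DE | Largest ICC = (DE − 1) / 12.5 |
|---|---|---|
| 0 | 1.106 | 0.008 |
| 0.3 | 1.579 | 0.046 |
| 0.5 | 2.211 | 0.097 |
| 0.7 | 3.685 | 0.215 |

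Reading (b) is also a larger effect than it looks. With equal baselines, each interaction deviation is half the corresponding T1 deviation, so an interaction f of 0.25 means f = 0.50 among the T1 means, twice the stated figure.

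**Step 6. Reading (c): individuals are randomised.** No design effect for cluster allocation applies. The one-way test at f = 0.25 with 135 has the power of 0.73 found in Step 2.

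**The case against.** The strongest reply is that no shortfall has been shown. Data Analysis compares change between groups, which is a group-by-time test. With f = 0.25 and correlation 0.5 that test keeps about 0.8 or more on 7 df up to an ICC of 0.10. A design effect may even be hidden in the 135, since 81 × 1.67 ≈ 135. Every ICC used here is assumed. The 7 df are also a choice made here, because the protocol names no centre-level analysis; in reading (a) they alone take power from 0.80 to 0.61 before any ICC is applied. If centres were randomised but analysed by mixed ANOVA with no centre term, the main hazard would be understated standard errors and false positives, not lost power. Finally, failure to reproduce 135 depends on convention: if f already absorbs the repeated-measures correlation, the interaction test needs 162, not 81.

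Much of this stands. Power may be adequate, reading (a) is only one calibration, and a clustering inflation, though nowhere stated, cannot be excluded. The 7 df apply if centres are allocated and the analysis respects that; a valid analysis of the declared design cannot avoid them by leaving out the centre.

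What the reply does not do is support the stated 80%. It succeeds only by supplying a test, an effect-size metric, a correlation and an ICC that the protocol does not give. It also leaves the conflict over the unit of randomisation untouched. A statistical analysis plan might add a centre term, but the power claim and its listed inputs are in the protocol and need correcting there.

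**Conclusion.** The point holds. The protocol declares cluster randomisation and claims 80% power from a derivation that states nothing about clusters, and its wording on allocation points to individuals. The claim is unsupported as written; it is not shown to be false.

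The size is conditional. For ICCs of 0.01 to 0.10 with 13.5 analysed per centre, power runs from 0.98 (interaction f = 0.25, correlation 0.5, ICC 0.01) down to 0.31 (135 calibrated to 80% without clustering, ICC 0.10), both on 7 df. The spread comes mainly from the unstated effect-size metric, correlation and ICC. The part that needs no assumption about ICC is the contradiction over the unit of randomisation and the absence of any stated clustering input. That 135 cannot be derived from the stated inputs without adding one also needs no ICC, though it rests on reading 0.25 as Cohen's f.

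**What to change.** 1. State in Design and in Participants, in the same terms, whether centres or individuals are randomised.
2. If centres: keep 150 participants. Restate the sample-size paragraph with the effect-size metric, the test matched to Data Analysis, the assumed correlation between time points, the ICC with its source, the number of centres per arm (10 do not divide equally into three), the cluster size and the design effect. Replace the unqualified 80% with the power, or the detectable effect, on between-centre degrees of freedom over a range of ICCs.
3. If individuals: remove the cluster label and re-derive 135 from a named test with all its inputs.

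The cost is protocol wording. No extra participants are required, but the reported power may turn out less favourable than 80%.

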### Assessment Procedures

After basic screening, assessments will be conducted by trained social services staff and trained research assistants employed by the University of Hong Kong for the intervention group.

Assessments will be conducted for all 3 arms at baseline (T0/Intake), completion of intervention (2 months, depending on individual condition) or drop-out (T1/Exit), and follow-up at 3 months (T2/FU) from discharge. Assessment will last for around 60 minutes for all participants.

### *Intervention*

#### ACT and Exercise:

Participants with chronic pain will participate in an intervention program given twice a week for 8 weeks. ACT designed for chronic pain will be conducted by register Clinical Psychologist, and co-facilitated by registered social workers who are trained by this project and employed by the NGOs. The trained peer supporters will be matched to individual older adults to walk them through the process with regular follow-up. Exercise training program would be designed and instructed by an Exercise Specialist and trained exercise coach.

#### Art and Exercise:

Similar to the experimental group, participants with chronic pain will participate in the sham program twice a week for 8 weeks. The Art program, conducted by an art therapist and research assistants, and will be co-facilitated by the project officers who are trained by this project and employed by the NGOs. Trained peer supporters will be matched to individual older adults to walk them through the process with regular follow-up if necessary. Exercise training program would be designed and instructed by an Exercise Specialist and trained exercise coach.

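### Peer follow-up is unconditional in the ACT and exercise arm but only as needed in the art and exercise sham arm, so the protocol permits less peer contact in the sham arm

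*Protocol*

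**What the plan says.** The Protocol describes the two active programmes in consecutive subsections under Intervention.

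- **ACT and Exercise**, on peers: "The trained peer supporters will be matched to individual older adults to walk them through the process with regular follow-up". The sentence ends there, with no condition.
- **Art and Exercise**, on peers: trained supporters are matched to individuals in the same words, but here they are to "walk them through the process with regular follow-up if necessary".

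The art arm is introduced in these terms: "Similar to the experimental group, participants with chronic pain will participate in the sham program twice a week for 8 weeks". The Design section also names a sham group among the three arms, and it sets ACT and exercise against two comparators: art and exercise, and treatment as usual. The primary outcomes are the BPI (pain intensity and interference) and the PHQ-9 (depressive symptoms).

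**The concern.** A sham arm is there to hold constant what is not specific to the treatment under test. Individual attention from a peer supporter is one such element. The Objectives section names ACT in combination with exercise as what is to be evaluated, and does not list peer support as part of it.

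If peers follow up regularly in one arm and only when someone judges it necessary in the other, participants may receive different amounts of personal attention for reasons unrelated to ACT or art. Both primary outcomes rest on the participant's own account of pain, its interference, and the frequency of depressive symptoms. Such accounts could respond to attention. A better result with ACT than with art could then partly reflect peer contact.

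Of the two comparisons, ACT versus art is the one that holds the session schedule, the exercise component and peer matching alike, so it is the one the discrepancy weakens. Contact that differed during the programme cannot be equalised afterwards by analysis.

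**Working it through.** The point rests on wording, and the plan gives no figure to reproduce. The two subsections compare as follows.

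| Element | ACT and exercise | Art and exercise | Same? |
|---|---|---|---|
| Sessions | Twice weekly, 8 weeks | Twice weekly, 8 weeks | Yes |
| Exercise | Exercise specialist and trained coach | Identical sentence | Yes |
| Peers matched to individuals | Yes | Yes | Yes |
| Peer follow-up | Regular, no condition | Regular, only if needed | **No** |
| Lead therapist | Clinical psychologist | Art therapist and research assistants | No |
| Co-facilitators | Registered social workers | Project officers | No |

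**Step 1: scheduled contact.** The ACT arm is to "participate in an intervention program given twice a week for 8 weeks", and the art arm has the same schedule. Sessions per arm = 2 per week × 8 weeks = 16. Difference = 16 − 16 = 0. Any contact gap must therefore come from outside the sessions.

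**Step 2: exercise.** Both subsections carry the sentence "Exercise training program would be designed and instructed by an Exercise Specialist and trained exercise coach". It adds no difference.

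**Step 3: peer sentences.** Apart from the opening article in the ACT subsection, the two sentences are the same until the art version adds its closing two-word condition. In the ACT arm, regular follow-up is due to every participant. In the art arm it is due only to those for whom it is judged necessary. A delivery team that follows each sentence exactly may give equal contact, or less contact in the art arm. The art rule does not require as much as the ACT rule.

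**Step 4: other text.** No other section sets a frequency of peer contact, says when follow-up counts as necessary, or equalises or records contact across arms. The discrepancy stands unresolved within the document.

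**Step 5: reach.** The wording bears on 1 of the 2 comparisons in the Design section, ACT versus art. ACT versus treatment as usual does not involve the art arm and is unaffected.

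**Step 6: size.** A contact gap would be the number of contacts per participant with ACT minus the number with art. Neither number is given, so neither the gap nor its effect on BPI or PHQ-9 can be calculated.

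**The case against.** The strongest reply is that this is an editorial query. The closing words may be loose drafting. Peers are matched in both arms, sessions are equal, and the wording is compatible with no difference in delivery at all. All of that stands, and it limits how much weight the point can bear.

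Three stronger readings are tempting, and the protocol does not support them.

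- **That the sham arm will receive less contact, or that the ACT effect is biased by some amount.** The text only permits less contact. Whether it happens, how much, and whether it moves the outcomes are all unknown.
- **That the protocol breaks a promise of equal attention.** The phrase likening the art arm to the experimental group introduces the sentence on the session schedule. Nowhere does the protocol state that peer contact is matched. The expectation of like treatment comes from the arm's role as a sham and from the parallel peer provision. It is an inference, though a reasonable one.
- **That peer follow-up is the only difference not required by the content of the arms.** Staffing differs too: "ACT designed for chronic pain will be conducted by register Clinical Psychologist, and co-facilitated by registered social workers", against "The Art program, conducted by an art therapist and research assistants, and will be co-facilitated by the project officers". The lead roles plausibly follow from content. The co-facilitators do not obviously do so, since social workers and project officers are both trained by the project and employed by the NGOs. Aligning the peer rule would therefore not isolate ACT content completely.

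It is also fair to object that regular follow-up is undefined in both arms, so deleting two words would leave two equally vague rules. That is correct, and it shapes the fix. What survives is narrow: the two arms carry different written rules for an element that both share, and the difference is easily avoided. Other differences between the arms do not excuse adding one more.

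**Conclusion.** The point holds as a cheap improvement to the design. The protocol sets an unconditional peer follow-up rule for ACT and exercise and a conditional one for art and exercise. This permits less peer contact in the sham arm and allows an avoidable attention difference in the ACT versus art comparison on BPI and PHQ-9. Its size cannot be derived.

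The conclusion assumes that delivery teams follow the sentences as written, and that peer follow-up is a non-specific element and not an intended part of ACT. The Objectives section is consistent with the second assumption, but the protocol does not say what follow-up consists of. If the closing words are a drafting slip and both arms are run alike, no harm results, but the text should still be corrected. Confidence is medium for that reason.

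**What to change.** 1. In the Art and Exercise subsection, delete the two-word condition at the end of the peer-supporter sentence.
2. State one peer follow-up schedule (how often and in what form) and apply it to both active arms. The deletion alone removes the written asymmetry but does not ensure equal contact.
3. Preferably, keep a simple log of peer contacts by arm, so that any remaining difference can be seen and reported.

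The cost is a short protocol edit, some extra peer time in the art arm (the documents do not allow an estimate of how much), and minor record keeping. Peer supporters are already trained and matched to individuals in both arms, so no new role is needed.

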### *Measurements*

Basic demographics including age, gender will be collected.

### *Primary Outcomes*

1. Feeling and Function in existence of pain: Brief Pain Inventory (BPI) (Cleeland, 1994) aims to evaluate the individual's pain experience and its effect on physical function on daily activities. The tool consists of 11 items, using an 11-point rating, of which 0 indicates not interference and 10 as interferes completely. The Cronbach's alpha coefficients for interference and severity subscales were .88 and 0.80 respectively (Cleeland, 1991). A validation on the Taiwanese population of BPI (BPI-T) was done by Ger et al in 1999.
2. Depression: The Patient Health Questionnaire (PHQ-9) (Kroenke, Spitzer, & Williams, 2001): a 9-item instrument that incorporates depression diagnostic criteria with other leading major depressive symptoms, and rates the frequency of the symptoms which factors into the scoring severity index. PHQ-9 scores of 5-9,

10-14, 15-19, 20 and above represent mild, moderate, moderately severe, and severe depression. The Cronbach's alpha coefficients for Primary Care Study and Ob-Gyn Study were .89 and 0.86 respectively. A validation on the Chinese version of PHQ- 9 was done by Yeung, Y. in 2010.

### *Secondary Outcomes*

3. Anxiety: Generalized anxiety disorder scale (GAD-2) (Plummer et al., 2016; Seo & Park, 2015): a 2-items self-report to determine the person's level of anxiety. Each item is rated on a 4-point scale ranging from 0 (not at all) to 3 (nearly everyday), where higher scores indicate higher anxiety levels. This scale has a Cronbach's alpha of 0.82 (Seo & Park, 2015). A validated Chinese version was done by Luo et al in 2019.
4. Psychological Flexibility: CompACT-SF (Morris, 2019), also known as CompACT-8 aims to evaluate the individual's psychological flexibility. The tool consists of 8 items, using a 7-point rating of which 0 represents strongly disagree and 6 as strongly agree, of which higher score represents higher psychological flexibility. The scale demonstrated internal reliability of ( $\alpha > .73$ ).
5. Pain Self-Efficacy-2 (PSEQ-2) (Nicholas et al., 2015): a 2-items self-report to evaluate the individual's confidence level in performing each of the activities despite of their pain. Each item is rated on a 7-point scale ranging from 0 (not at all confident) to 6 (completely confident), of which higher scores indicate stronger self-efficacy. This instrument has a Cronbach's alpha coefficient of 0.76. A validation on the Chinese version of PSEQ-2 was done by Yang et al. in 2019.
6. Quality of life: SF-12 Health Survey (Luo, 2003): a 12-items self-report to evaluate the person's quality of life based on the scores of 2 subscales: Physical component score (PCS) and Mental component score (MCS). The scale has a Cronbach alpha coefficient of 0.77 for PCS-12 and 0.80 for MCS. A validation on Hong Kong Chinese was done by Lam et al in 2005.

